#### **Phase II, months 20 – 31: Enhanced Referral/Linkage to Care condition.**

The Enhanced Referral/Linkage to Care condition follows the same steps as described in the Standard Care described above if there is imminent risk. If there is no imminent risk, the JJ intake worker contacts the CSC program directly for a "warm hand-off". The CSC intake worker will speak with the parent and arrange for an intake evaluation, either at the CSC clinic or at the family's home. For families that are already receiving mental health treatment, the JID intake worker will arrange the referral to the CSC for a consultation, at the CSC or family home. After the appointment is arranged, the JID intake worker reviews some psychoeducation material about the role of

mental health care in emotional/behavioral problems (see below).

In addition, the CSC clinician who takes the phone call will use a motivational interviewing style to encourage families to follow up with their scheduled appointment. This portion of the protocol is based on a module from PI [name]/Co-I [name]'s protocol that was recently tested in two randomized controlled trials (MH01783; AA020705) that are nearing completion (see below).

**Psychoeducation material.** The JID intake worker will review a handout on common symptoms of emotional distress and how youth and parents benefit from seeking mental health services. More specifically, the document outlines how to recognize warning signs of emotional distress, and the importance of finding support for difficulties that interfere with functioning and quality of life. We decided to use a generic description of emotional problems, including some psychosis-like experiences as well as other common concerns, rather than a description of specific psychosis-spectrum symptoms, because we believe it is more consistent with the level of training of JID workers and avoids the premature implication of a psychotic disorder diagnosis. In addition, to ensure these procedures can be easily disseminated in the future if they appear useful, we kept this aspect of the protocol very straightforward. The JID Intake worker will just be asked to read through the handout with the parent and not required to learn any interview material about mental health care or psychosis-spectrum symptoms. The review of the psychoeducation material will be presented with the goal of enhancing the chances that the family will follow through with the CSC appointment.

**Motivational interviewing prompts.** Similar to the psychoeducation aspect of the protocol, the CSC clinician will not be required to learn any interview material but instead will have a sheet with the following prompts adapted from motivational interviewing protocols by Drs. [name] and [name]. The decision to keep this aspect of the protocol very structured was to ensure its eventual disseminability. Prompts include:

*Do you think it is necessary for your child to be seen at the clinic?*

*May I share a few concerns I have?*

*Some teens who have thoughts such as [specify] often get worse as they get older. For many teens, it's only temporary and they start to feel better after they start talking to someone.*

*And for some teens there are medicines that can help with these thoughts quite a bit.*

*Getting help for these thoughts early is important so we really encourage parents to get it checked out.*

*How are you feeling about going to the clinic appointment?*

*What might get in the way of you being able to do that (i.e., transportation, insurance, time of day)?*

*Is there anything we can do to help make it easier for you to get to the appointment?*

*We can call you the day before or the morning of the appointment to remind you -- would you like that?*

**Follow-up reminders to set up a CSC appointment.** Three and seven days after the referral to CSC, the JJ intake worker will text the teen's parent/caregiver to see if the family kept their appointment with the CSC. If not, the intake worker will text the parent the phone number for the CSC and will also ask permission to contact the CSC to further assist the family in setting up another appointment. JID workers can also choose to contact families by phone. A record of contacts will be recorded in order to examine feasibility, acceptability, and efficiency of these procedures.

[figure not shown]
**Training JID and CSC workers in Enhanced Referral protocol (months 18 -19).** A one hour training in this protocol will be conducted to mimic the type of training that would occur in typical circumstances. For the JID intake workers, we will: 1) review the MAYSI-2 Thought Disturbance subscale and PQ-B and discuss why these symptoms might be potentially significant for these youth; 2) review the handout about symptoms of mental health problems in youth as well as the importance of a follow-up evaluation; 3) review the concept of the CSC and why a referral to the CSC would be potentially helpful to the adolescent; 4) review the need to arrange a referral to the CSC for a consult even if the youth is already receiving mental health care elsewhere; and 5) role play the "warm hand-off" procedures used when referring families to the CSC.

There will be no ongoing supervision of the JID intake worker because that would be the most likely situation in a typical JJS intake department. Instead, we will: 1) as part of routine staff meetings, the JID intake workers will be reminded about screening for mental health problems with the MAYSI-2/PQ-B and the referral procedures for youth flagging in on any problem, i.e. substance use, suicidal ideation, or thought disturbance; 2) have the JID intake workers complete procedural checklists at the end of the interview that prompt them to follow referral procedures (we have had success with improving procedures with this type of self-monitoring in two recently completed RCTs); 3) as part of the research procedure, in their daily review of MAYSI -2 and PQ-B forms, research staff will identify anyone who screened positive on these measures and check with the JID intake workers about whether they completed the self-monitoring checklist, reviewed the handout with the parents and made a direct referral to the CSC. This procedure serves as a feedback mechanism to JID staff and as a reminder to complete the referral protocol with youth.

**Fidelity to the Enhanced Referral/Linkage to Care condition.** We will have the CSC clinician, who will be employed by the research project but also work at the CSC, audiotape their conversation with the family in the enhanced referral phase of the study. The CSC clinician will use a hand-held audio recorder so that only the CSC clinician's portion of the conversation will be recorded. Fidelity will also be rated by interviewing the parent/caregiver at the baseline research assessment, which will typically occur within a week of the JID

appointment. Caregivers will be asked what the CSC intake worker said to them about scheduling a CSC appointment. The RA conducting the assessment will record verbatim the parent's responses. In both the clinician reported and parent reported data collection, fidelity will be rated by PI [name] and Co-Is [name] and [name] on a two-point scale (0= not satisfactory; 1= satisfactory). If there is disagreement, a consensus meeting will be held to resolve discrepancies in ratings.

**Baseline and follow-up assessment.** Families in both phases of the study will complete the same assessments at baseline and 3-month follow-up to gather data on treatment history, psychosis-spectrum symptoms, general psychiatric symptoms and functioning, as well as JJS contacts (see details below under Measures). In addition, at follow-up, we will interview families about barriers to treatment linkage and treatment satisfaction. The RA and Co-I [name] will be blind as to whether the families were seen for follow-up CSC or mental health care until after the interviews are completed.

We will also interview JID intake workers and CSC staff to assess both services and implementation factors related to referral process and completion. The baseline and follow-up assessment battery were designed to minimize participant burden and to thoroughly assess psychosis-spectrum symptoms. The follow-up assessment will be scheduled 3-months post-referral to the CSC. The 3-month follow-up period will allow us to assess whether high risk youth engage in treatment with the CSC or other mental

healthcare. Both baseline and follow up interviews will be conducted in-person and last approximately 1.5- 2 hours.

Co-I [name] will administer the Structured Interview for Psychosis-risk Syndromes (SIPS), described below. She has received formal training and certification by SIPS developers to conduct the interviews, and she was trained to research quality reliability (ICC>.8) within her prior research team. She will administer all the SIPS interviews in order to maintain consistency across the two phases of the study as well as across participants. At baseline, when we will assess youth with both positive and negative screens, Co-I [name] will be "blind" to whether youth have screened positive or negative. At follow-up, she will know that all youth have screened positive on the MAYSI-2 and *PQ-B*, but the RA and Co-I [name] will instruct families not to disclose whether they followed through with the referral to the CSC or whether they have received any type of follow-up mental health care until after the assessment is completed.

**Training in assessment.** Training in the assessment protocol will occur during the first 2 months by Co-I [name], following procedures we used in other RCTs. Under Co-I [name]'s oversight, research staff conducting baseline assessments will also receive training on working in the JJS and on how to appropriately respond to logistical questions that participants' may have about the JJS. Co-I [name] will oversee the baseline assessment and Co-I [name] will oversee the follow-up assessment component of the protocol. If parents request it, the results of the evaluation will be shared with the CSC in both phases of the study.

**Procedures for mental health deterioration/safety concerns.** It is possible that some participants will report symptoms during their research assessment that may warrant additional mental health care. If any youth indicates serious psychotic symptoms or suicidal/homicidal thoughts, a safety plan will be established by Co-[name]. Either [name], [name], [name], or [name] all licensed clinical psychologists, will be notified and review the safety plan. In all cases, if families are in treatment at the CSC, or a mental health clinic, a mutually agreeable plan will be derived with the CSC clinical team. In the event of an acute crisis, patient will be transferred to the Rhode Island Hospital (RIH) psychiatric Emergency Department, where all the PI and Co-Investigators [name] and [name] have staff appointments and clinical privileges (See **Human Subjects**).

**Measures.** The selection of measures was designed to be realistic for the court system with an emphasis on eventual implementation in a larger effectiveness trial. All assessments will be administered via laptops

using REDCap (Research Electronic Data Capture), a secure web-based application. An advantage of computer-administered self-report assessments is that participants using this medium have been found to be more comfortable disclosing personally sensitive information and to be less likely influenced by social desirability in their responses. Using REDCap instead of traditional pencil and paper measures will also save time and labor that would otherwise be required for data entry, double entry, and resolution of discrepancies. To ensure participant safety, all items will be reviewed by research staff before the end of the assessment in case there is a need to review responses with the youth or caregiver.

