**Early psychosis intervention through Coordinated Specialty Care.** Given the rise in recognition of psychosis-risk syndromes and the promising benefits of early psychosocial care, specialized psychosis-spectrum intervention services are being established across the nation. Coordinated Specialty Care (CSC) intervention programs offer tailored services to clients with psychosis-spectrum disorders to help individuals effectively manage early symptoms and comorbid concerns (e.g., difficulties related to mood, anxiety, attention, and substance abuse), preserve functioning, and reduce the long-term impact of illness. As stated in

the FOA, "CSC treatment involves integrated, team-based care and typically features use of single antipsychotic medications, prescribed in low doses; family psychoeducation; supported employment and/or education; cognitive-behavioral therapy oriented to recovery; coordination with primary care services; and continuity of care across inpatient and outpatient treatment settings". Rhode Island has two CSC clinics funded by the 2014 SAMSHA set-aside in the Community Mental Health Block Grant Program grant to the state. In this research project, we will partner with the CSC based at the Kent Center, the mental health clinic based in Warwick, RI, which is the second largest city in the state and only a 15-minute drive for families that live in Providence, RI, where the largest JID is located. The CSC based in Warwick, called the Healthy Transitions program, uses a team approach to provide case management, family psychoeducation, individual and group therapy, coordination of mental health and primary care by a nurse clinician, psychiatry consultation, substance abuse specialty care, employment and education counseling, and wraparound case management. *The CSC accepts patients regardless of insurance status; schedules evaluations typically within 2 weeks; provides evening appointments and can be reached by public transportation. Families can be reimbursed for travel costs.* (See letter of support from [name], Program Director).

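### Both scheduled Phase II texts can fall before the CSC visit they ask about, so the two-contact efficiency count partly measures booking delay

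*Combined protocol and SAP*

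**What the plan says.** Three places in the combined protocol and SAP set the sequence.

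- **Booking.** Under Phase II (Enhanced Referral/Linkage to Care condition), the appointment is made during the hand-off call: "The CSC intake worker will speak with the parent and arrange for an intake evaluation". Its date is therefore normally known at referral.
- **Waiting time.** The Research Strategy paragraph on Coordinated Specialty Care says that the clinic "schedules evaluations typically within 2 weeks". It gives no distribution.
- **Follow-up.** The Phase II paragraph on follow-up reminders says: "Three and seven days after the referral to CSC, the JJ intake worker will text" the parent or caregiver. The text is sent "to see if the family kept their appointment with the CSC". The only other branch reads "If not, the intake worker will text the parent the phone number for the CSC and will also ask permission to contact the CSC", and the purpose is "to further assist the family in setting up another appointment".

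The same paragraph lets intake workers phone families if they choose, and says that contacts will be logged. Its heading describes the texts as reminders for setting up an appointment, although by then one has been arranged. The Data Analysis Plan (Aim 2B) defines efficiency as the number of texts and calls needed before a referral is completed, with two contacts as the benchmark.

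**The concern.** The clock for the texts starts at the referral, while the event they ask about happens on a booked date that may lie up to about two weeks later. Take a family booked for day 10. It has not kept its appointment on day 3 or on day 7, because the appointment has not yet come. Read literally, both texts lead to the branch that offers help with a further appointment, although nothing has been missed. If the family then misses day 10, no text is scheduled to find out.

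Two things are at stake. One is the follow-up component itself, whose scheduled checks may precede the event they check. The other is the efficiency measure. The number of scheduled texts equals the benchmark of two, so a late booking alone can bring a family to that number. This study is a planning grant meant to refine procedures for a larger trial, so a feasibility measure that is hard to interpret is a real loss.

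**Working it through.** The plan states no figure that depends on this point, so there is nothing to reproduce. The check compares the contact days with the booking window.

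**Inputs from the documents**
- Scheduled contacts: days 3 and 7 after referral (Phase II, follow-up reminders).
- Booking window: typically up to 14 days (Research Strategy, Coordinated Specialty Care).
- Phase II enrolment goal: 70 (Estimated sample size and retention rates).
- Efficiency benchmark: 2 contacts (Data Analysis Plan, Aim 2B).

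**Assumption.** The shape of the waiting time is not given, so several shapes are tried. Let D be the booked day. The share still pending after day t is P(D > t):
- even over 0–14 days: 1 − t/14
- front-loaded triangular on 0–14 days: (1 − t/14)²
- back-loaded triangular on 0–14 days: 1 − (t/14)²
- exponential with 90% or 80% seen by day 14: 0.1^(t/14) or 0.2^(t/14)

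| Assumed shape | Pending after day 3 | Pending after day 7 | Of 70, if all are booked |
|---|---|---|---|
| Even | 11/14 = 79% | 7/14 = 50% | 35 |
| Front-loaded | (11/14)² = 62% | 0.5² = 25% | 17.5 |
| Back-loaded | 1 − 9/196 = 95% | 1 − 0.25 = 75% | 52.5 |
| Exponential, 90% by day 14 | 61% | 32% | 22 |
| Exponential, 80% by day 14 | 71% | 45% | 31 |

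For the families in the day-7 column, both scheduled texts come before the visit and none comes after it.

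**Effect on the efficiency count.** Suppose every family attends as booked, the texts change nothing, and contacts are counted up to the attended visit. A visit by day 3 scores 0, a visit after day 3 and up to day 7 scores 1, and a later visit scores 2. The mean count is P(D > 3) + P(D > 7):
- even: 0.786 + 0.500 = 1.29
- front-loaded: 0.617 + 0.250 = 0.87
- back-loaded: 0.954 + 0.750 = 1.70

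The mean doubles (0.87 to 1.70) through booking dates alone.

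**Two families that each needed one contact after a miss.** The first is booked for day 2, misses, rebooks after the day-3 text and attends on day 6: count 1. The second is booked for day 10, misses, and rebooks after one optional phone call: count 2 + 1 = 3. The need was the same, but if the benchmark means two or fewer, only the first family meets it.

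**The case against.** The best defence is practical. A worker told that the visit is next Tuesday would not rebook it, and an early text to a family with a pending visit serves as a reminder, which suits the paragraph's heading. Intake workers may phone at any time. The section on youth in the juvenile justice system says that intake coordinators typically monitor diverted youth for 90 days, including adherence to referrals. CSC clinicians also offer a reminder call shortly before the visit. Finally, this is a pilot that logs contacts in order to learn how the procedure works.

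Much of this stands. A reader might infer that misses after day 7 can never be noticed or acted on. The documents do not support that: phoning and monitoring are both open routes. What is absent is a scheduled text.

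The defence does not remove the point. The phone contact is optional, undated and not tied to the visit. The CSC reminder precedes the visit, so it cannot detect a miss. Common sense has to carry the rule, because the one-hour training does not list these texts, the procedural checklist is completed before either text is due, and intake workers have no ongoing supervision. Sensible conduct would also leave the efficiency count as it is: a text sent before the visit still counts.

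One limit remains. A figure follows this paragraph and is not visible in the text reviewed. If it shows a later scheduled contact, the point narrows accordingly.

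**Conclusion.** The mismatch is real and moderate. For any visit booked after day 7, both scheduled texts precede the visit and no scheduled text follows it. The affected share cannot be fixed from the documents. It is about 50% of booked families if bookings are even over 14 days, and about 25% to 75% under front- or back-loaded shapes. With all 70 Phase II enrollees booked, that is about 35 families (roughly 18 to 53). The consequence is that the Aim 2B count partly reflects booking delay, and reaching two contacts says little about whether the texts helped.

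Two stronger readings are tempting and do not hold. The first is that the log will hold false records of missed appointments: the plan says only that contacts are recorded and counted, and no section codes attendance from the texts. The second is that the Aim 2A linkage result is misclassified, or its 80% mark put out of reach. Attendance data also come from the CSC with consent (CMIR client level mechanisms). The plan does not credit the linkage gain to these texts either: the warm hand-off, home evaluation, psychoeducation, motivational prompts and reminder calls all act before any miss. No loss of linkage can be calculated from the documents.

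**What to change.** Reconcile the Coordinated Specialty Care paragraph, the Phase II hand-off text and the follow-up reminders paragraph, including its heading, so that they describe one consistent sequence for an appointment already booked. The contact timing and the rule for acting on a reply are for the investigators to settle.

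For measurement, add two fields to the existing contact log: the booked date, and the status at each contact (not yet due, kept or missed). In Aim 2B, report contacts before and after the booked date separately when judging the two-contact benchmark.

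The cost is protocol wording, two log fields and a split efficiency table. It needs no extra staff and does not change the Aim 2A analysis.

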### **2. CMIR implementation level measures**

These data will be collected and measures will be administered to JID staff and administrators at the conclusion of Phase II of the project.

**Feasibility** will be defined as the percent of youth who screen positive on the MAYSI-2 Thought Disturbance subscale and/or PQ-B who receive the Enhanced Referral/Linkage to Care protocol in Phase II of the project. Follow-up rates of texting/phone calls will also be examined separately with respect to its feasibility.

**Penetration** will be measured by the percent of *personnel* who are trained to deliver the Enhanced Referral/Linkage to Care condition brief intervention.

**Acceptability** will be assessed using qualitative interviews with JJ staff related to their perceived roles in screening and using the Enhanced Referral/Linkage to Care protocol. In addition, the *Attitudes Toward Mental Health Screening*, a 15-item scale that assesses clinician’s attitudes towards and self-efficacy in relation to screening and intervention, will be administered at baseline and follow-up. The measure has 4 subscales: positive attitudes, level of confidence, perceived barriers, and role congruence towards mental health screening. Staff rate each item on a five-point scale from “not at all” to “a very great extent”.

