**Aim 2B: Identify implementation and service level factors that promote/hinder linkage to the CSC.** Feasibility and Penetration, the number and percentage of JID personnel trained and consistency (% of time) using the enhanced referral protocol will be calculated with descriptive statistics. A rate of 80% will be the benchmark. Efficiency will be rated by the number of text message and phone contacts necessary to complete the referral to the CSC. A benchmark of two contacts will be considered an indicator of efficiency. Equity of enhanced referral protocol fidelity and treatment linkage across gender, race, and ethnicity will be compared across Phase I (Standard Care) and Phase II (Enhanced Referral/Linkage to Care condition), as well as cross-sectionally in the Enhanced Referral/Linkage to Care condition only, using cross-tabulation approaches. Acceptability. JJS staff perceived roles in screening and referral will be reported in percentages based on qualitative interviews as well as by mean, median, and range of scores on the Attitudes toward Mental Health

Screening measure. A total of 80% of the JID personnel scoring within one standard deviation of the mean on this measure based on the literature will be the benchmark.

**Aim 3A: Investigate client level factors at follow-up.** Attitudes about CSC referrals. These analyses follow the qualitative interview procedure described above. Rates of treatment initiation/retention in CSC services or other mental health care. Percentages of CSC participation will be calculated with 80% set as the benchmark as will other types of mental health care as rated on the CASA. For those already in mental health care at the time of enrollment, percentages of consultation to the CSC will be calculated, as will the types of treatment received and frequency/intensity of the services. Treatment barriers and motivation. Scores on the *Motivation for Youth's Treatment Scale* and the *Barriers to Treatment Participation Scale* will be analyzed using a paired t-test to determine any changes in these measures from baseline to three month follow-up. Treatment Satisfaction. These analyses follow the qualitative interview procedure described above.

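### The 80% feasibility benchmark does not separate protocol delivery prompted by research staff from unprompted delivery by intake workers

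*Combined protocol and SAP*

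**What the plan says.** The section on training JID and CSC workers in the Enhanced Referral protocol states: "There will be no ongoing supervision of the JID intake worker". The reason given is that a typical department would have none. Three substitutes follow: reminders at routine staff meetings, a checklist that the worker completes, and a check by research staff, which is labelled a research procedure. In the third, staff find every positive screen "in their daily review of MAYSI -2 and PQ-B forms" and "check with the JID intake workers about whether they completed the self-monitoring checklist", reviewed the handout and referred directly to the CSC. The stated function is: "This procedure serves as a feedback mechanism to JID staff and as a reminder to complete the referral protocol with youth".

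Under CMIR implementation level measures, feasibility "will be defined as the percent of youth who screen positive on the MAYSI-2 Thought Disturbance subscale and/or PQ-B" and "who receive the Enhanced Referral/Linkage to Care protocol in Phase II of the project". In the Data Analysis Plan, Aim 2B summarises feasibility and penetration through the personnel trained and "consistency (% of time) using the enhanced referral protocol", and adds: "A rate of 80% will be the benchmark".

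Neither section says when delivery is scored relative to the check, or asks for prompted delivery to be identified. The record of contacts described under follow-up reminders covers texts and calls to families, not prompts to workers.

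**The concern.** The purpose of the feasibility figure is to show whether intake workers will use the protocol under conditions that other courts could reproduce. The plan applies that standard elsewhere. Under Design Consideration it rejects a prior evaluation by the court clinic, and CSC staff meeting families at the JID, because neither is typical. A case-by-case check by research staff with an office on the same hallway is not typical either.

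If a youth who received the protocol only because of the check counts the same as one who received it unprompted, a result at or above 80% cannot be read as routine use. That matters because the pilot is meant to prepare a larger effectiveness-implementation trial.

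A second consequence concerns Aim 2A. The check is described only for the enhanced condition, so it coincides with phase. The Phase II minus Phase I difference in completed referrals may include its effect, and covariate adjustment cannot separate the two.

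**Working it through.** **Inputs from the protocol.** More than 900 juveniles are screened a year and about 11% flag for thought disturbance, given as N = 99 (Estimated sample size and retention rates). The benchmark is 80% (Aim 2B).

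**Inputs that are assumed.** The protocol gives neither of these:
- u, the proportion of positive-screen youth who would receive the protocol without the research check, taken over 40% to 75%;
- s, the share of missed cases completed because of the reminder, taken over 25% to 75%.

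**Step 1. The plan's figures.** 900 × 0.11 = 99, which reproduces the stated N. The 80% is a chosen threshold with no derivation, so there is nothing to reproduce. Since 0.80 × 99 = 79.2, meeting it takes 80 youth. Youth positive only on the PQ-B would add to the 99.

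**Step 2. How often the reminder operates.** 99 / 52 = 1.9 a week. The form review is daily, but a reminder follows a positive screen, so it occurs about twice a week on the MAYSI-2 figure.

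**Step 3. Rescue needed to reach 80%.** Observed rate = u + (1 − u) × s. Setting this to 0.80 gives s* = (0.80 − u) / (1 − u).

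| Unprompted use u | s* |
|---|---|
| 40% | 0.40 / 0.60 = 67% |
| 50% | 0.30 / 0.50 = 60% |
| 60% | 0.20 / 0.40 = 50% |
| 70% | 0.10 / 0.30 = 33% |
| 75% | 0.05 / 0.25 = 20% |

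**Step 4. Chance of meeting the benchmark.** Exact binomial probability of at least 80 of 99, treating youth as independent:

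| u | s | Observed rate | P(at least 80 of 99) |
|---|---|---|---|
| 50% | 0 | 50% | <0.001 |
| 50% | 50% | 75% | 0.11 |
| 50% | 75% | 87.5% | 0.98 |
| 60% | 0 | 60% | <0.001 |
| 60% | 25% | 70% | 0.01 |
| 60% | 50% | 80% | 0.48 |
| 60% | 75% | 90% | 0.998 |
| 70% | 0 | 70% | 0.01 |
| 70% | 25% | 77.5% | 0.26 |
| 70% | 50% | 85% | 0.90 |

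The answer depends on s. With little rescue the benchmark is still missed. With substantial rescue, a routine rate well below 80% would be reported as a pass. The table shows what is possible; it does not estimate what will happen.

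**Step 5. Phase I.** The Standard Care section describes no check with workers on whether the referral was made. The overview of study procedures does describe daily hand-in of forms and a back-up route for missed youth, but that route leads to research staff contacting the family about the study. It is not described as prompting the worker to refer to the CSC.

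**The case against.** A reader might infer that feasibility is scored after the reminder. The documents do not say so. The check is itself an inquiry, and the worker's answer would naturally give status before that reminder has acted on that case, so the plan could be carried out correctly as it stands. What remains is that it does not commit to this.

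A reader might also infer a large rescue effect. The workflow argues against one for the same youth. The hand-off is meant to happen while the family is at the JID, the handout is read with the parent, and the checklist is completed at the end of the interview. The form review probably comes after the family has left. A late reminder could produce a later referral but would not easily restore an in-person hand-off. This stands, and is why no value of s can be defended from the documents.

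If the check works mainly as feedback, it changes how later youth are handled, so pre-reminder status is already shaped by earlier checks. This stands too, and limits what any re-scoring can show.

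On Aim 2A, the check is listed with the staff-meeting reminders and the checklist as what replaces supervision, so it can be read as part of the Phase II package. Aim 2A compares packages, and completed referrals also depend on families. The documents therefore do not support calling the contrast wrong. They support only that the research-staff component should be named.

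**Conclusion.** The point holds as a gap in definition and recording. The plan sets out to mirror a department without supervision, adds a case-level research reminder, and defines its feasibility measure so that prompted and unprompted delivery count alike. A pass at 80% could then reflect research prompting in part.

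The size cannot be determined from the documents. Under the assumed values, reaching 80% requires rescue of half the misses if unprompted use is 60%, and one third if it is 70%. The binomial figures rest on 99 youth, independence between them, and assumed u and s. The documents do not support saying that the benchmark will be met because of the reminders, or that the Aim 2A difference is a research-staff effect of any given size.

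This does not invalidate a descriptive pilot. It should be settled before Phase II starts, because status before the reminder must be captured at the time and cannot be reliably reconstructed later.

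**What to change.** 1. At each check, record and time-stamp the status of the checklist, the handout and the direct CSC contact before any reminder is given.
2. Apply the 80% benchmark to pre-reminder status and report post-reminder status alongside it.
3. State that pre-reminder status is still an upper bound on routine use, because feedback on earlier cases carries over to later youth. This assumes that feedback does not reduce use.
4. For Aim 2A, state that the Phase II package includes the research-staff check, for which Phase I has no described equivalent. Add an analysis that counts referrals made only after a reminder as not completed. Label it a worst-case bound, not an unbiased estimate, since some of those referrals would have been made later without a prompt.

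The reminder itself can stay. The cost is one added data item at a check that staff already make, and a feasibility figure that will probably be lower.
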